#### List of Abbreviations

ACT Acceptance and Commitment Therapy

CBT Cognitive-Behaviour Therapy
CFT Compassion-Focused Therapy

# **Background: The Impact of Chronic Pain**

Chronic pain is pain that lasts longer than 3 months and affects 18% of the Scottish population (NHS QIS, 2008). Unlike acute pain, it is not an indication of sinister disease processes. In the process of learning to live with chronic pain, people may have experiences of being disbelieved by family, friends and health professionals, struggle with beliefs of being a burden on their loved ones and feel disappointment at not being able to fulfil previously held roles in the family (Smith & Osborn, 2007). Chronic pain becomes a stigma and these experiences, in conjunction with debilitating physical symptoms, can have a profound impact on mood, behaviour and general wellbeing. It is not the intensity of the pain that affects quality of life; the issue is more relational, for example, the negative beliefs that someone may hold about their pain (Lamé et al., 2005). Negative cognitions and emotions are activated by pain-related difficulties and multi-disciplinary treatments for chronic pain target the management of these internal experiences and daily functioning, rather than attempting to eliminate the physical sensation of pain.

### **Current Treatment Models in Chronic Pain**

Alongside education and physical exercise, Cognitive Behaviour Therapy (CBT) and Acceptance and Commitment Therapy (ACT) are used across multidisciplinary pain management programmes in the treatment of chronic pain. CBT is recommended by the Scottish Intercollegiate Guidelines Network (SIGN) Guideline 136 and ACT is recommended by the American Psychological Association (APA Division 12: Society of Clinical Psychology).

CBT aims to identify, examine and alter the impact of distressing, unhelpful cycles of cognition and behaviour. Techniques such as graded activation and graded exposure are also used to help achieve sustainable levels of activity and reduce avoidance (Williams et al., 2012; Bailey et al., 2010). Mediator analyses have identified self-efficacy as the mechanism of change in CBT for chronic pain (Turner et al., 2007), which is a construct targeted by many other psychotherapies, not only CBT. Acceptance and Commitment Therapy (ACT) aims to develop mindfulness, willingness to experience undesirable internal experiences and foster

distance between the self and negative thoughts. The overall process underlying the methods used in ACT can be conceptualised as 'psychological flexibility' (Hayes et al., 1999). A review by Hughes and others (2017) examined 11 trials, finding significant medium to large effect sizes for measures of acceptance and psychological flexibility.

Comparisons between individuals on an ACT and a CBT pain management programme has not uncovered significant differences across improvements sustained in pain interference, depression, anxiety, and quality of life (Wetherall et al., 2011). Gaudinano (2009) notes that more attention should be focused on the mechanisms of action as opposed to pitting separate treatments against each other and drawing conclusions about their efficacy based on differences across outcomes. Many psychotherapies share constructs and are often shown to result in similar outcomes.

# **Psychological Flexibility**

Cross-sectional studies do not give explanation into the direction of the relationship between process and outcome variables; it is difficult to deduce if outcomes have improved because psychological flexibility has increased, or if psychological flexibility has increased because the outcomes have improved. A number of cross-sectional studies have, however, proven that psychological inflexibility is linked to anxiety, depression and wellbeing (e.g. Masuda & Tully, 2011). Vowles and others (2014) performed correlation and regression analyses and reported significant relationships between psychological flexibility and measures of disability, emotional functioning, pain acceptance and valued activity. Four key process variables of psychological flexibility were investigated by McCracken and Gutierrez-Martinez (2011): pain acceptance, values-based action, psychological acceptance and mindfulness. General acceptance was found to show the largest effect size, predicting gains in outcome more so than those accounted for by pain acceptance. The authors note that the concept itself is a tricky idea to capture accurately, because behaviour related to psychological flexibility cannot be measured until one has a concept of psychological flexibility, which affects measurement of the baseline.

# **Self-Compassion**

Compassion-focused therapy (CFT) was developed for individuals who struggle with shame and self-criticism (Gilbert, 2009), both of which can be conceptualised as examples of distressing private experiences in the ACT model. It aims to promote a compassionate internal relationship with the self, drawing on the ability to view distressing experiences with kindness, understanding and shared humanity (Neff, 2003). Shame involves a negative evaluation of the *self*, unlike guilt, which involves a negative evaluation of *behaviour* (Lutwak et al., 2003). These complex emotions and cognitions are relevant in the context of chronic pain because of the experience in losing and adjusting to an identity. Purdie and Morley (2016) note that chronic pain is frequently invalidated by society and this constant negative social evaluation can result in a shameful appraisal of a person's sense of self. In this sense, CFT targets self-acceptance in the same way as ACT, but from a different perspective by bringing social inclusion into awareness.

The positive influence of self-compassion is beginning to be investigated across a range of long-term health conditions, such as diabetes (Friis et al., 2015) and cancer (Pinto-Gouveia et al., 2014). To date, however, there is little research on self-compassion and chronic pain.

Wren and others (2012) found that self-compassion was a significant predictor of mood, negative pain beliefs and disability related to pain. This cross-sectional study indicated that self-compassion may be significant in predicting pain adjustment, but can only comment on association and not causal relationships. The authors suggest that future research in this area could examine interventions specifically designed to promote self-compassion. Marshall and Brockman (2016) reported self-compassion to significantly correlate with processes of psychological flexibility, and self-compassion actually predicted mental wellbeing over and above psychological flexibility. This indicates that combining these therapies may result in improved treatment outcomes. This study was, however, conducted on a non-clinical population which may limit generalisability. Empirical research examining links between these two constructs is limited.

#### Rationale

There is a need for evidence-based answers to explain why and how psychological interventions are successful (Kazdin, 2007). Multimodal treatments are becoming the norm and breaking down these components to examine individual efficacies is not a good use of resources (Wicksell et al., 2010). CFT offers a complementary approach to be used alongside current interventions, targeting the inevitable feelings of shame and self-criticism in the process of adjusting to chronic pain. A strong correlation between self-compassion and psychological flexibility has already been established, and gaining insight into the direction of the relationship between these concepts and treatment outcome would be the next logical step. By focusing on mechanisms of change, better theories can be developed and may promote treatment efficacy (e.g. by matching to patient need). This would be a far more efficient way to develop interventions, whilst maintaining a person-centred delivery of care.

## **Principal Research Question**

 Do self-compassion and psychological flexibility mediate change in a Compassion-Focused Therapy group for adults with chronic pain?

# **Secondary Research Questions**

- Which is the better predictor of change - self-compassion or psychological flexibility?

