# Sample Size

Fritz and MacKinnon (2007) propose guidelines for recommended sample sizes in order to detect mediation effects with .8 power. These guidelines are informed by existing literature in the field. There is less robust research on self-compassion and chronic pain, therefore, this calculation is based on research in psychological flexibility and chronic pain.

McCracken and Gutierrez-Martinez (2011) conducted correlational analyses on the processes of psychological flexibility following a group intervention based on ACT. These processes included acceptance of pain, mindfulness, psychological acceptance and values-based action (r values between 0.33 and 0.55). These positive correlations indicate that the group intervention was related to higher levels of psychological flexibility.

A review by Hayes and others (2006) identified several studies that reported correlational effect sizes between acceptance, and depression/anxiety/daily functioning related to chronic pain (r = -0.58/-0.66/0.47 respectively). These negative correlations illustrate that higher levels of psychological flexibility were related to better outcomes.

Based on these correlational effect sizes, Fritz and MacKinnon's guidelines suggest that a sample size of 53-71 is required.

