## **Analysis**

The analysis will focus on the proposed mediating factors (self-compassion and psychological flexibility) and how they explain the outcome of the CFT-incorporated group intervention. In order to study the processes of change, this study will measure change in mediators and outcomes over the course of the group.

In a mediation model, the effect of the independent variable (IV; CFT group) on a dependent variable (DV; outcome/change in symptoms) is conveyed through a third mediating variable. In order to be a mediator, a variable must change during the intervention, be associated with the intervention, and have an impact on the outcome.

In this study, it is hypothesised that self-compassion and/or psychological flexibility are the mediating variables that explain the influence of the group intervention on eventual outcome, i.e. the overall change in symptoms at the end of the group. Linear regression and nonparametric bias-corrected bootstrap, which corrects for skew in the data, will be applied to the data using SPSS, using the PROCESS macro. An effect of mediation will be indicated if the confidence interval does not contain zero.

Missing data will be handled using either the maximum likelihood or multiple imputation method, as recommended in literature.

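### The secondary question asks which of two correlated mediators is the better predictor, but the plan states neither a joint model nor a comparison between them

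*Combined protocol and SAP*

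**What the plan says.** The Secondary Research Questions section of the combined protocol and SAP asks "Which is the better predictor of change - self-compassion or psychological flexibility". The Rationale states that "A strong correlation between self-compassion and psychological flexibility has already been established", without giving a figure.

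The Analysis section says "it is hypothesised that self-compassion and/or psychological flexibility are the mediating variables". It defines mediation as an effect that "is conveyed through a third mediating variable", which is a single-mediator description. On method it says "Linear regression and nonparametric bias-corrected bootstrap, which corrects for skew in the data, will be applied to the data using SPSS", with the PROCESS macro. Its one decision criterion is "An effect of mediation will be indicated if the confidence interval does not contain zero".

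The section does not say whether the two mediators share a model. It gives no contrast of indirect effects, no comparison of standardised coefficients or explained variance, and no rule for when both intervals, or neither, exclude zero.

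The Sample Size section relies on published guidelines for "recommended sample sizes in order to detect mediation effects with .8 power" and concludes that these "guidelines suggest that a sample size of 53-71 is required". That target concerns detecting a mediated effect, not a difference between two.

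**The concern.** The question is comparative, but the rule tests one indirect effect at a time against zero. If only that rule is available, the natural way to rank the mediators is to see whose interval excludes zero, and that is not a test of the difference between them.

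With correlated mediators the gap can go wrong in two ways, depending on how it is filled. In separate models, each mediator picks up part of the other's effect, so an inert one can look like a mechanism of change. In a joint model that borrowing is removed, but each slope becomes less precise, so which of two equal mediators reaches significance is largely chance. The first problem also affects the principal question, because it changes what is attributed to each mediator. The second affects the secondary question.

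**Working it through.** **Inputs from the document.** Sample size 53-71, power .8, correlations of .33 to .55 (intervention to flexibility processes) and of .47 to .66 in absolute value (acceptance to outcomes), all from Sample Size; bias-corrected bootstrap, from Analysis.

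**Assumed inputs.** 95% two-sided interval; correlation r between the mediators of .5 to .8, with .2 to .3 as a sensitivity range; equal a-paths (mean change 0.5 SD, or .39 in a between-person version); slopes as given below. The documents do not state these.

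**1. The plan's own figure.** One mediator, M = aX + e and Y = bM + e, with a bias-corrected bootstrap of ab. At n = 53 with assumed a = .39 and b = .59, power is .81. At n = 71 with the document's lowest pair, a = .33 and b = .47, power is about .785. So 53-71 is consistent with about .8 power for one mediator.

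**2. Two mediators.** Y = b1·M1 + b2·M2 + e, each mediator with unit variance and correlation r. Each indirect effect is the mean change (or a-path) times the slope. Fitted alone, M2 has expected slope b2 + r·b1. Two cases:
- Inert M2 (b1 = .5, b2 = 0, r = .7): fitted alone, M2's slope is .7 × .5 = .35, although its own effect is zero.
- Equal mediators (b1 = b2 = .3, r = .7): fitted alone, each slope is .3 × 1.7 = .51. Fitted together, each is .3, with sampling variance inflated by 1/(1 − .49) = 1.96.

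**3. One active, one inert mediator.** Mean-change version, 1,000 simulated trials per row:

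| n | r | Inert credited, separate | Inert credited, joint | Contrast detects the difference |
|---|---|---|---|---|
| 53 | .7 | 69.4% | 8.4% | 31.9% |
| 53 | .8 | 79.2% | 8.0% | 25.8% |
| 71 | .5 | 56.9% | 8.5% | 54.3% |
| 71 | .7 | 80.0% | 8.0% | 41.7% |
| 71 | .8 | 89.4% | 9.6% | 33.3% |

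A further set of mean-change runs at r = .5/.6/.7 gave 53/66/77% separately at n = 53 and 62/79/88% at n = 71, with 7-10% jointly. Taken together, r of .5-.7 gives roughly 50-88% for separate models and about 7-11% for a joint model. Including the between-person version and r up to .8 widens these to 29-89% and 6-10% in that set of runs. At r of .2-.3 the separate-model rate is about 14-32%.

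**4. Two equal mediators: exactly one interval excludes zero.**

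| Version | n | r | Separate | Joint | Contrast (false difference) |
|---|---|---|---|---|---|
| Mean change, slopes .3 | 53 | .7 | 10.2% | 62.4% | 7.2% |
| Mean change, slopes .3 | 71 | .5 | 6.3% | 56.4% | 7.0% |
| Mean change, slopes .3 | 71 | .7 | 4.3% | 67.3% | 8.1% |
| Between-person, slopes .39 | 71 | .5 | 12.9% | 35.6% | 6.8% |
| Between-person, slopes .39 | 71 | .8 | 8.0% | 68.6% | 8.1% |

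Across all runs at slopes of about .3 or more, the false-winner rate is roughly 36-69% for the joint model read by intervals, about 1-23% for separate models, and about 4-11% for the contrast.

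**5. Power of the contrast with one mediator inert.** About 18-70% over n = 53-71, depending on r, the slopes and the version of the model.

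Monte Carlo error is at most about √(.5 × .5/1000) = 1.6 percentage points per cell.

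**The case against.** The strongest reply is that the plan is silent rather than wrong. It does not say the mediators are analysed separately; the single-mediator sentence can be read as a textbook definition; the hypothesis names both mediators; and PROCESS can fit them in parallel. A reader might infer that following the plan as written necessarily credits inert mediators. The documents do not support that: in a joint model the rate is only about 7-11%. This part of the point is therefore conditional on separate models. It does not rescue the plan, because a joint model without a contrast is where false winners are most common.

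A reader might also infer that separate models would often rank two equal mediators by chance. Rates of 25-33% at n = 53 and 18-29% at n = 71 do arise, but only with slopes of .2 each and a mean change of 0.4 SD. The slope of each mediator fitted alone is then .2 × 1.5 = .30 to .2 × 1.7 = .34, weaker than the .47 to .66 correlations used in Sample Size. Nearer those planning values the rate is about 1-23%.

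Three further objections stand in part. The strong correlation has no figure, and the text does not say that changes in the two measures are correlated. The simulated estimators are supplied here, because the independent variable named in Analysis, the CFT group, is constant in a single-group design. Finally, better predictor could mean a regression comparison rather than a larger indirect effect; linear regression is named, and the Self-Compassion section cites a non-clinical study that found self-compassion predictive beyond flexibility. But no criterion is given for that comparison either.

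**Conclusion.** The point holds as a gap in specification that misleads on either way of filling it. A comparative question is asked, and the only stated rule is not comparative. If the mediators are fitted separately, the main harm is false credit to an inert mediator: roughly 50-88% of trials at r of .5-.7 in the mean-change runs, less in some between-person variants, and about 14-32% at r of .2-.3. If they are fitted jointly and ranked by intervals, the main harm is a false winner between equals: roughly 36-69%, against about 4-11% with a direct contrast. The two harms belong mainly to different models and should not be attributed to one.

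The absence of a comparison rule is read from the text. Every percentage depends on the assumed correlations, slopes, mean changes and form of model, so they show direction and rough size and do not predict this study's error rates. The pages between the Analysis section and the References were not available, and nothing is assumed about them. This is a cheap improvement to the plan.

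**What to change.** Amend the Analysis section to:
- enter both mediators, standardised, in one parallel-mediator model, and say how the path from the intervention to each mediator is estimated in a single group. If that path is a mean change, scale by a standard deviation without centring, since centring would remove the change;
- judge each mediator by its specific indirect effect in that model;
- answer the secondary question with the bootstrap confidence interval for the difference between the two indirect effects;
- state that if this interval includes zero, the conclusion is that the mediators are not distinguishable at this sample size, and neither is called the better predictor;
- label the comparison exploratory.

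The cost is SAP wording and one extra estimate from data already being collected. The drawback is a less decisive answer: contrast power of about 18-70% at n = 53-71, even when one mediator is inert, makes an inconclusive result likely.

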## Methodology

# **Participants**

Participants will be adults with chronic pain who attend and complete the CFT-incorporated groups at the Lothian Chronic Pain Service / Pain Management Programme.

Inclusion Criteria	Exclusion Criteria
- Chronic Pain lasting a minimum of 3	- Active substance misuse
months	
 
Active suicidality
 

 
Fluency of English sufficient for
 
	- Terminal illness
participation in the group and	
 
Inability to provide informed
 

completion of questionnaires	consent (as defined by the Five
- Aged 18+ (no upper age limit)	Statutory Principles of the Mental

- Ability to provide informed consent	Capacity Act, Code of Practice,
as judged by the clinical team	2007)

# Design

This study will follow a within-group (non-randomised) effectiveness-implementation design (Curran, 2012). Five self-report measures will be completed by participants at three specified time periods (pre-, mid- and post-group; see *Procedure* below).

#### Recruitment

2-3 new Pain Management Programme groups start every month, each running for 11 weeks at the Astley Ainslie Hospital in Edinburgh. 6 groups run every week and each group is booked for a maximum of 15 people. These groups are run by at least two qualified members of the clinical team (Clinical Psychologists and Physiotherapists). There will be no need to advertise the research outwith normal clinical operations because clinical staff will offer all group participants the opportunity to participate in the research during their initial assessment, and data collection will overlap with existing routine outcome measures.

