### Intervention

All groups will follow the same 11-week, structured timetable, using Compassion-Focused Therapy. As there are no current guidelines for using CFT in chronic pain, exercises have been adapted from 'Compassion Focused Therapy for Dummies' (Welford, 2016), incorporating the key elements of CFT (Gilbert, 2009).

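### Treatment is given in therapy groups but the mediation analysis makes no allowance for grouping, so the deciding interval may be too narrow, depending on the ICC, the number of groups and the estimand

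*Combined protocol and SAP*

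**What the plan says.** In the combined protocol and SAP, the Recruitment section describes how treatment is delivered: "2-3 new Pain Management Programme groups start every month, each running for 11 weeks". On the number and size of groups it says "6 groups run every week and each group is booked for a maximum of 15 people". Staffing is set out in the same section: "These groups are run by at least two qualified members of the clinical team". There is no comparator (Design: "This study will follow a within-group (non-randomised) effectiveness-implementation design"), and content is common to all groups (Intervention: "All groups will follow the same 11-week, structured timetable").

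The Analysis section states the method: "Linear regression and nonparametric bias-corrected bootstrap, which corrects for skew in the data, will be applied to the data using SPSS", through the PROCESS macro. It gives one decision rule: "An effect of mediation will be indicated if the confidence interval does not contain zero". The confidence level is not stated. The Sample Size section concludes from a published guideline for .8 power that "a sample size of 53-71 is required".

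The available text does not mention a therapy-group identifier, an ICC, a design effect, a multilevel model, cluster-robust errors or resampling by group. It does not give the number of groups to be included or the expected consent and completion rates, although the Procedure section restricts the analysis to completers.

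**The concern.** Members of one therapy group share facilitators, group dynamics and calendar time, so their changes on mediator and outcome may be correlated. Ordinary regression and the usual bootstrap, which resamples individuals, count each participant as an independent observation. If the correlation is positive, an interval for any quantity that contains a mean change is too short. Exclusion of zero is the only stated criterion, so the shortfall would turn directly into false claims of mediation.

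There is a second route. If groups that do well on the mediator also do well on the outcome for reasons of their own, the mediator-outcome slope mixes individual-level and group-level association.

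**Working it through.** **1. The plan's own figure.** The range 53-71 is a look-up in a table that the document does not reproduce, so it cannot be derived from the text. As a check, bootstrap power was simulated with the correlations in the Sample Size section used as coefficients (.33 to .55 for the first path, .47 to .66 in absolute value for the second). At N=71, the pair (.33, .47) gives 0.81. At N=53, (.33, .66) gives 0.71, (.55, .47) gives 0.90 and (.55, .66) gives 0.96. The figure is plausible for independent participants. Nothing in it allows for grouping.

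**2. Number of groups.** At full booking: 53/15 = 3.5, so at least 4; 71/15 = 4.7, so at least 5. If only 6 per group were analysed (assumed): 53/6 = 8.8, so 9; 71/6 = 11.8, so 12.

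**3. Design effect for a mean change**, 1 + (m-1) x ICC, with assumed ICCs:

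| Group size m | ICC | Design effect | Effective N from 53 | Effective N from 71 |
|---|---|---|---|---|
| 15 | .01 | 1.14 | 46.5 | 62.3 |
| 15 | .05 | 1.70 | 31.2 | 41.8 |
| 15 | .10 | 2.40 | 22.1 | 29.6 |
| 6 | .01 | 1.05 | 50.5 | 67.6 |
| 6 | .05 | 1.25 | 42.4 | 56.8 |
| 6 | .10 | 1.50 | 35.3 | 47.3 |

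**4. Design effect for a slope**, 1 + (m-1) x ICC(mediator) x ICC(outcome), with equal ICCs and independent group effects. At m=15: 1 + 14 x .05 x .05 = 1.035, and 1 + 14 x .10 x .10 = 1.14. This is far smaller than for a mean.

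**5. Simulating the decision rule.** Mediator change = a + group effect + individual error. Outcome = b x mediator + a separate group effect + individual error. Each group effect has variance equal to the ICC, and the total error variance is 1. The indirect effect is mean mediator change x slope. Intervals are 95% bias-corrected (the level is assumed) and resample individuals, over 1,500 trials of 800 resamples.

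| Layout | Quantity | ICC 0 | .01 | .05 | .10 |
|---|---|---|---|---|---|
| 5 groups of 14 | False mediation (a=0, b=.59) | 8.5% | 9.7% | 15.9% | 25.7% |
| 5 groups of 14 | Coverage (a=.39, b=.59) | 0.94 | 0.93 | 0.88 | 0.83 |
| 12 groups of 6 | False mediation (a=0, b=.59) | 7.3% | 9.7% | 12.3% | 14.3% |
| 12 groups of 6 | Coverage (a=.39, b=.59) | 0.95 | 0.95 | 0.92 | 0.90 |
| Both | Coverage, slope only (b=0) | 0.94-0.95 | 0.93-0.94 | 0.93-0.94 | 0.93-0.94 |

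Monte Carlo error is about 1 point: sqrt(.16 x .84/1500) = .009. Further runs at similar settings gave 7-8%, 16-18% and 22-25% for 6 groups of 12, and 6-7%, 11-13% and 14-16% for 12 groups of 6, at ICC 0, .05 and .10. The excess over 5% at ICC 0, some 2-3 points, belongs to the bias-corrected bootstrap and not to grouping.

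**6. Correlated group effects.** With 6 groups of 12, true slope 0 and an assumed correlation of .7 between a group's effects on mediator and outcome, one run gave slope error of 7.5% at ICC .05 and 9.1% at .10 (about 6-10% overall). With group indicators it was 5.3% and 4.6%.

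**7. Does a remedy work with so few groups?** A slope with group indicators, a t-interval on group means for the mediator change, and a Monte Carlo interval for the product gave false mediation of about 4-6% when the mediator did not change, with 6 or 12 groups.

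**The case against.** The strongest reply is that no ICC is given, and that one site and one timetable make a low value possible. At ICC .01 the added error is only 1-2 points. This stands. A reader might infer that the intervals are too narrow as a matter of fact, or that there are only a handful of groups. The document supports neither: 4-5 groups is a minimum at full booking, and low consent or completion could spread the sample over 9-12.

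A reader might also take the 22-26% as the error rate of the plan as written. That holds only if the indirect effect contains the mean mediator change. The Analysis section does not say how treatment becomes a variable in a single-arm study. The correlations behind the sample size, and the secondary question about the better predictor, suggest slopes between participants, which are little affected. On the other side, the Analysis section requires a mediator to move over treatment and to be linked to it. Without a comparator, mean change is the natural reading of that path. Both readings remain open.

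Group-level confounding is likewise a possibility and not a finding. Groups that improve on both measures may be part of how a group therapy works. Group indicators remove that variation and so change what the slope means.

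Finally, group-level inference is costly even if the ICC is zero. The t multiplier for a mean rises by 59% with 4 groups (3.182/2.007), 39% with 5 (2.776/1.994) and 29% with 6 (2.571/1.994). This stands and must be disclosed.

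**Conclusion.** The omission is real and should be corrected. Treatment is wholly in groups, and neither the stated analysis nor the sample size allows for it. The interval that decides mediation may therefore be too narrow; the document does not allow a firmer statement.

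For n of about 70-72, assumed ICCs of 0, .05 and .10, and mean mediator change as one factor of the indirect effect, false mediation is about 8%, 16% and 22-26% with 5-6 groups, and about 7%, 12% and 14-16% with 12. If only the between-participant slope matters, the effect is slight unless group effects on mediator and outcome are correlated. These results also assume a 95% two-sided level and resampling of individuals, which is the ordinary form of the bootstrap; the plan does not name the resampling unit.

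**What to change.** 1. Record the therapy-group identifier for each participant. State the expected number of groups and define the path from treatment to mediator.
2. Enter group indicators as fixed effects in the regression of outcome on mediator, and say that the slope is then a within-group slope. The cost is small. The width factor is about sqrt((n-1)/(n-k)) for k groups: sqrt(52/49) = 1.03 for 4 groups and n=53, and sqrt(70/59) = 1.09 for 12 groups and n=71, so intervals are about 3-9% wider.
3. Where mean mediator change is part of the indirect effect, estimate it with a random intercept for group and small-sample degrees of freedom. A t-interval on group means is equivalent only when group sizes are equal. Form the indirect-effect interval from the two estimates, for example by a Monte Carlo interval for the product. Cluster-robust errors or a cluster bootstrap would themselves be unreliable with so few groups.
4. Show the individual-level bootstrap as a sensitivity analysis, and report the estimated ICC and the number of groups.
5. State in the Sample Size section that the .8 power for 53-71 makes no allowance for grouping. For a mean change in groups of 15, keeping the same information at ICC .05-.10 would need 53 x 1.70 = 91 to 71 x 2.40 = 171 participants (rounded up).

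Steps 1 to 4 need SAP wording and one variable that should be known from group bookings. The real cost is power. For a 0.5 SD mean change, slope .5 and ICC .05, detection falls from about 96-98% to 75-79% with 6 groups, and from about 97% to 89-91% with 12. The higher figures rest on an inflated error rate. More, smaller groups reduce the loss.
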